#### 2.6. Site Pooling

Analysis centers will be created by totaling the number of subjects at each site and pooling smaller sites together.

Sites with fewer than 8 subjects will be pooled. Sites will be sorted by country, the number of subjects at that site in descending order, and then site number in ascending order. For each country separately, the site at the top of the list (the largest site with less than 8 subjects and, if tied, the smallest site number) will be pooled with the site at the bottom of the list (the smallest site with less than 8 subjects and, if tied, the subjects and, if tied, the largest site number). If the pooled site now has at least 8 subjects, it is removed from the list.

RD.06.SPR.18252 - FINAL October 23, 2017

Otherwise, it will continue to be combined with the smallest available site until it has at least 8 subjects or no sites remain.

After all possible pooling is done, if all remaining small sites cannot be pooled together into an analysis center with at least 8 subjects, those sites will all be pooled into the analysis center created in the previous iteration of the pooling, even if that analysis center is not the smallest. If there was no other pooling done (because all small sites in the country total to less than 8 subjects), those sites will be pooled with the smallest site in the country. If no other sites are available in that country, the site will remain with fewer than 8 subjects.

#### 3. Protocol Deviations

Protocol deviations will be provided in the DV SDTM dataset. Subjects with a deviation categorized as "Major" or "Major for face" will be excluded from the PP dataset. Subjects with a deviation categorized as "Major," "Major for face," or "Major for trunk" will be excluded from the PPT dataset.

The number of subjects in each analysis population will be summarized, and specific protocol deviations will be summarized in a listing.

#### 4. Disposition

For the purposes of disposition summaries, subjects are considered to be Screened if they have signed the Informed Consent form. Subjects will be considered randomized once they've been assigned a treatment.

#### 5. Prohibited Medications

Prohibited medications will be flagged on the concomitant medications listing. A list of prohibited medications with ATC/Drug names will be identified prior to the database lock.

#### 6. Efficacy Analyses

#### 6.1. IGA/PGA Success Rate

Success rate of IGA and PGA will be calculated for each visit. Success rate will be calculated as the number of subjects considered a success at that visit divided by the number of subjects with IGA/PGA data at that visit.

The large-sample approximation for binary data will be used for the 95% confidence intervals around the difference in success rates. Continuity corrections will not be used for either the CMH test or the generation of 95% confidence intervals.

The success rate of IGA and PGA using missing data procedures will be presented at Week 12. The success rate of IGA and PGA will be presented at each visit using the observed data; no missing data imputation will be used.

In addition, overall success rate at Week 12 will be calculated using missing data procedures assuming that the data is missing at random. Overall success rate is defined as having an IGA score of "clear" or

"almost clear" at Week 12 and a grade change of at least two from baseline and having a PGA score of "clear" or "almost clear" at Week 12 and a grade change of at least two from baseline.

#### 6.2. Multiple Imputation – Missing at Random

A multiple imputation method will be used to account for missing data on efficacy analyses. The following steps will be followed:

- For lesion counts, the pattern of missingness in the data will be evaluated. If the data is not monotone missing, the MCMC method will be used to make it monotone missing. The single chain method will be used, with 200 burn-in iterations and 100 iterations between imputations. Fifty imputations will be created. The seed number will be 18252. Lesion counts generated as a result of the MCMC method will be re-imputed if they are below zero; they will not be rounded.
- 2) The MI procedure in SAS will be used to create multiple imputations of the data that have no missing values. If the MCMC method was previously employed, one imputation will be made using each of the fifty MCMC-imputed datasets. If the MCMC method was not used, fifty imputations will be created using the MI procedure assuming the data is Missing at Random. The seed number will be 18252. These imputations will use the following models:
  - a. For IGA and PGA scores, a logistic regression model will be used with covariates for treatment and non-missing data from earlier scheduled time points including baseline. Weeks will be imputed sequentially, with IGA/PGA data at prior non-baseline weeks treated as continuous data (baseline will be treated as categorical).
  - b. For lesion counts, a linear regression model will be used with covariates for treatment and non-missing data from earlier scheduled time points including baseline.
- 3) The imputed datasets will be analyzed as follows:
  - a. For IGA and PGA scores, the number of successes at Week 12 will be analyzed using the CMH test stratified by analysis center. The sample difference in proportions and its standard error will also be calculated. No continuity corrections will be used.
  - b. For lesion counts, change from baseline to Week 12 in lesion counts will be analyzed using an ANCOVA model with covariates for baseline count, analysis center, and treatment.
- 4) The resulting analysis on the imputed datasets will then be combined to produce a single set of statistics.
  - a. For IGA and PGA scores, the results from the CMH analysis will be combined using the procedure by Rubin (1987) and Li et al. (1991) to produce a pooled CMH statistic and p-value. The differences in proportions and standard errors will be combined using the MIANALYZE procedure in SAS; the resulting pooled difference and standard errors will be used to produce 95% confidence intervals based on the large-sample approximation method for binary data without the use of a continuity correction. Both methods will be used as described in the Bohdana Ratitch et al. paper *Combining Analysis Results from Multiply Imputed Categorical Data*.
  - b. For lesion counts, results from the ANCOVA analysis will be combined using MIANALYZE procedure in SAS.

Below is an example of the SAS syntax for the MCMC and logistic MI procedures for IGA/PGA:

```
proc mi data=transI seed=18252 out=miI1 nimpute=50 noprint;
class trt01pn baseline week 1;
var trt01pn baseline week 1;
monotone logistic(week 1=trt01pn baseline);
run;
proc mi data=miI1 seed=18252 out=miI2 nimpute=1 noprint;
by IMPUTATION ;
class trt01pn baseline week 2;
var trt01pn baseline week_1 week_2;
monotone logistic(week_2=trt01pn baseline week 1);
run;
proc mi data=miI2 seed=18252 out=miI3 nimpute=1 noprint;
by _IMPUTATION_;
class trt01pn baseline week 4;
var trt01pn baseline week_1 week_2 week_4;
monotone logistic(week 4=trt01pn baseline week 1 week 2);
run;
proc mi data=miI3 seed=18252 out=miI4 nimpute=1 noprint;
by _IMPUTATION_;
class trt01pn baseline week 8;
var trt01pn baseline week 1 week 2 week 4 week 8;
monotone logistic (week 8=trt01pn baseline week 1 week 2 week 4);
run;
proc mi data=miI4 seed=18252 out=miI(rename=(_imputation_=imp)) nimpute=1 noprint;
by _IMPUTATION_;
class trt01pn baseline week_12;
var trt01pn baseline week 1 week 2 week 4 week 8 week 12;
monotone logistic(week_12=trt01pn baseline week_1 week_2 week_4 week_8);
run:
```

Below is an example of the SAS syntax for the MCMC and linear MI procedures for lesion counts:

```
proc mi data=transI seed=18252 out=mcmcI(rename=_imputation_=imp) nimpute=50 minimum=0 noprint;
mcmc impute=monotone chain=single nbiter=200 niter=100;
var baseline week_1 week_2 week_4 week_8 week_12;
run;
```

```
proc mi data=mcmcI seed=18252 out=miI nimpute=1 minimum=. 0 0 0 0 0 0 noprint;
by imp;
class trt01pn;
var trt01pn baseline week_1 week_2 week_4 week_8 week_12;
monotone reg(week_12=trt01pn baseline week_1 week_2 week_4 week_8);
run;
```

#### 6.3. Multiple Imputation – Missing Not at Random

As a sensitivity analysis, the multiple imputation process will be repeated assuming that the data is missing not at random. This process will be the same as the one described for the Missing at Random analysis, but with the assumptions changed. The Missing Not at Random dataset will use data collected from vehicle subjects to impute missing observations.

Below is an example of the SAS syntax for the logistic MI for IGA/PGA for the missing not at random assumption:

```
proc mi data=transI seed=18252 out=miI1 nimpute=50 noprint;
class trt01p baseline week_1;
var baseline week_1;
monotone logistic(week_1=baseline);
mnar model(week_1 / modelobs=(trt01p="Vehicle"));
run;
```

```
proc mi data=miI1 seed=18252 out=miI2 nimpute=1 noprint;
by _IMPUTATION_;
class trt01p baseline week_2;
var trt01p baseline week_1 week_2;
monotone logistic(week_2=baseline week_1);
mnar model(week_2 / modelobs=(trt01p="Vehicle"));
run;
```

```
proc mi data=miI2 seed=18252 out=miI3 nimpute=1 noprint;
by _IMPUTATION_;
class trt01p baseline week_4;
var trt01p baseline week_1 week_2 week_4;
monotone logistic(week_4=baseline week_1 week_2);
mnar model(week_4 / modelobs=(trt01p="Vehicle"));
run;
```

```
proc mi data=miI3 seed=18252 out=miI4 nimpute=1 noprint;
by _IMPUTATION_;
class trt01p baseline week_8;
var trt01p baseline week_1 week_2 week_4 week_8;
monotone logistic(week_8=baseline week_1 week_2 week_4);
mnar model(week_8 / modelobs=(trt01p="Vehicle"));
run;
```

```
proc mi data=miI4 seed=18252 out=miI(rename=(_imputation_=imp)) nimpute=1 noprint;
by _IMPUTATION_;
class trt01p baseline week_12;
var trt01p baseline week_1 week_2 week_4 week_8 week_12;
monotone logistic(week_12=baseline week_1 week_2 week_4 week_8);
mnar model(week_12 / modelobs=(trt01p="Vehicle"));
run;
```

Below is an example of the SAS syntax for the MCMC and linear MI procedures for lesion counts for the missing not at random assumption:

```
proc mi data=transI seed=18252 out=mcmcI(rename=_imputation_=imp) nimpute=50 minimum=0 noprint;
mcmc impute=monotone chain=single nbiter=200 niter=100;
var baseline week_1 week_2 week_4 week_8 week_12;
run;
proc mi data=mcmcI seed=18252 out=miI nimpute=1 minimum=. 0 0 0 0 0 0 noprint;
by imp;
class trt01p;
var baseline week_1 week_2 week_4 week_8 week_12;
monotone reg(week_12=baseline week_1 week_2 week_4 week_8);
mnar model(week_1 / modelobs=(trt01p="Vehicle"));
mnar model(week_2 / modelobs=(trt01p="Vehicle"));
mnar model(week_8 / modelobs=(trt01p="Vehicle"));
mnar model(week_8 / modelobs=(trt01p="Vehicle"));
mnar model(week_12 / modelobs=(trt01p="Vehicle"));
```

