# 7.4.2.2 Handling of dropouts or missing data

The primary method of imputation for missing data will be MI (Multiple Imputation) using the Missing At Random (MAR) assumption.

Galderma R&D RD.06.SPR.18252 Page 18 of 25

For the primary MAR based multiple imputation, the MI procedure of the SAS system will be used to generate sets of data with missing values imputed from observed data. It is expected that the pattern of missing data will be monotonic, with slight deviations being corrected by the Markov Chain Monte Carlo (MCMC) method of the MI procedure.

Linear regression will be employed to model the missing lesion count data and a logistic regression model will be used for the ordinal IGA/PGA scores, with the following covariates included in the imputation model: treatment and non-missing data from earlier timepoints. IGA/PGA success will be calculated from the imputed IGA/PGA scores. The imputed datasets will be analyzed using the methodology described in Section 7.4.1.1 for changes in lesion counts, and IGA/PGA success. The results from the analysis of the multiple imputed datasets will be combined by the MIANALYZE procedure of the SAS system. The seed number to be used will be the protocol number (18252) and the number of imputation is planned to be 5.

For success rate, the final p-value from the CMH test stratified by analysis center on each multiply imputed dataset will be generated using the Schafer, J. L. Multiple Imputation Methodology. The final difference of success rate between treatment groups (CD5789 50  $\mu$ g/g – Vehicle) and the final 95% confidence interval of the difference from each multiply imputed dataset will be generated using the method by Bohdana Ratitch ed. al..

For changes in lesion counts, the final p-value, treatment difference (CD5789 50  $\mu$ g/g – Vehicle), and the 95% confidence interval of the treatment difference from the ANCOVA model on each multiply imputed dataset will be generated from the MIANALYZE procedure of SAS.

To assess the robustness of the primary efficacy results, the following sensitivity analyses will be also conducted:

a. The same imputation method above will be repeated based on the Pattern-Mixture Model under the missing not at random (MNAR) assumption, by using the profiles from vehicle subjects with observed data to impute missing data.

b. LOCF (Last observation carry forward) approach

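### The example code for the lesion-count MNAR analysis omits `week_4` and lists `week_8` twice, so at Week 4 it does not follow the vehicle-based rule in the text; the numerical effect is minor

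*SAP*

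**What the plan says.** Main SAP section 7.4.2.2 (repeated under the sensitivity analyses in 7.4.1.1) defines a pattern-mixture sensitivity analysis that works "by using the profiles from vehicle subjects with observed data to impute missing data". Section 7.4.1.2 extends the same sensitivity methods to the truncal endpoints. Section 6.3 of the SAP addendum restates the rule: "The Missing Not at Random dataset will use data collected from vehicle subjects to impute missing observations". None of these places exempts a visit.

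Addendum 6.3 then gives code, introduced as follows: "Below is an example of the SAS syntax for the MCMC and linear MI procedures for lesion counts for the missing not at random assumption". The regression statement is "monotone reg(week_12=baseline week_1 week_2 week_4 week_8", so Week 4 is a predictor of Week 12, and treatment is not in the model. The vehicle-model lines are, in order:

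1. "mnar model(week_1 / modelobs=(trt01p='Vehicle"
2. "mnar model(week_2 / modelobs=(trt01p='Vehicle"
3. "mnar model(week_8 / modelobs=(trt01p='Vehicle"
4. the same `week_8` line again
5. "mnar model(week_12 / modelobs=(trt01p='Vehicle"

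The IGA/PGA code just above, in the same section, sets the vehicle model at Weeks 1, 2, 4, 8 and 12, once each.

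**The concern.** The point of this analysis is that subjects with missing data follow the vehicle profile and take no benefit from responses observed in the active arm. A visit left out of the vehicle-model lines does not follow that rule. Because treatment is not a covariate, a missing Week 4 count is then drawn from a regression fitted to active and vehicle subjects together, and the value is carried into the later visits.

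The analysis is one of the named robustness checks for two of the three co-primary endpoints (facial inflammatory and non-inflammatory counts) and for the two truncal counts. A programmer who copies the listing would run something other than what the text states.

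**Working it through.** **Line audit.**

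| | Visits |
|---|---|
| Post-baseline visits in the variable list | 1, 2, 4, 8, 12 |
| Vehicle-model lines, lesion counts | 1, 2, 8, 8, 12 |
| Vehicle-model lines, IGA/PGA | 1, 2, 4, 8, 12 |

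Week 4 is missing and Week 8 is duplicated. Repeating an identical line serves no purpose, and no text gives Week 4 a different treatment.

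**What the omission does.** The listing writes out the regression only for `week_12`. I take the earlier visits to be regressed on the variables before them in the list. At Week 4 the fitting set is then all subjects with an observed count, from both arms. The same pooled model is applied to active and to vehicle subjects with a missing count, so values in both arms move in the same direction.

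**Size.** The plan gives no figure for this, so the inputs are partly assumed.

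- From SAP section 6: differences of 3 and 6 lesions, SDs of 12 and 20, 600 per arm, and 16% overall for drop-outs and non-evaluable subjects.
- Assumed: correlation 0.8 between adjacent visits, falling off by powers; treatment effect reaching 20, 40, 60, 85 and 100% of its final size at Weeks 1, 2, 4, 8 and 12; all dropouts leaving after Week 2; dropout of 16% in one arm and 5% in the other.

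An approximate formula for the shift in the Week 12 treatment difference (code minus text; negative favours CD5789) is

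shift = −(a − v) × s × (e4 − r·e2) × r²

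where a and v are the dropout proportions in the active and vehicle arms, s is the active share of subjects observed at Week 4, e2 and e4 are the effects at Weeks 2 and 4, and r = 0.8. The factor r² carries a Week 4 value through Week 8 to Week 12.

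- Inflammatory: e4 − r·e2 = 1.8 − 0.8 × 1.2 = 0.84.
- Non-inflammatory: 3.6 − 0.8 × 2.4 = 1.68.
- For 16% active and 5% vehicle, s = 504/(504 + 570) = 0.469. Shift = −0.11 × 0.469 × 0.84 × 0.64 = −0.028 inflammatory, and −0.055 non-inflammatory.
- For 5% active and 16% vehicle, s = 570/1074 = 0.531. Shift = +0.031 and +0.063.
- For equal dropout, a − v = 0 and the shift is 0.

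**Simulation check.** 300 replicates per scenario, 600 per arm, regression-mean imputation, same assumptions:

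| Dropout, active / vehicle | Inflammatory | Non-inflammatory |
|---|---|---|
| 16% / 5% | −0.03 | −0.05 |
| 5% / 16% | +0.03 | +0.06 |
| 16% / 16% | 0.00 | 0.00 |

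A separate simulation with random draws (6 imputations) gave −0.038 (SE 0.007) and −0.055 (SE 0.011) for 16% versus 5%. With a wider assumed split of 24% active versus 8% vehicle, all missing by Week 4, and correlation 0.6 or 0.8, the shift was −0.03 to −0.04 and −0.05 to −0.08.

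**Scale.** The standard errors of the differences are 12 × √(2/600) = 0.69 and 20 × √(2/600) = 1.15 lesions. A shift of 0.03 is 0.03/0.69 = 4% of the first, and 0.06 is 0.06/1.15 = 5% of the second.

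**The case against.** The strongest case against is that this is one digit in a listing labelled an example. The prose rule is clear and consistent, and SAP section 9 says that SAS code details will be documented with the table shells, which are a separate document. The text available here was also machine-read: the block lacks the closing statement that the other blocks have, and other listings show damaged characters, so a 4 read as an 8 cannot be excluded. Only one of several supportive analyses is touched, and Week 12 itself keeps the vehicle model.

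Most of this stands, and it limits the weight of the point. The mismatch inside section 6.3 remains, because the listing as it reads does not do what its own text says. The listing also carries another sign of imperfect copying: a minimum-value list with seven entries for six variables.

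Three stronger readings are tempting, and the documents do not support them.

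- A reader might infer that the code is biased towards CD5789. The pooled Week 4 model also lends active-arm response to vehicle dropouts, so the two effects cancel at equal dropout and the sign reverses if the vehicle arm loses more subjects early. The SAP gives one overall 16%, not dropout by arm.
- A reader might infer that the sensitivity analysis actually run departs from the text. An example listing does not show what the production program does.
- A reader might infer that correcting the line makes every imputed value vehicle-based. The MCMC step before it, which fills intermittent gaps, uses both arms without a treatment term, and the correction does not change that.

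**Conclusion.** Wrong as written, of minor severity. The omission of Week 4 from the vehicle-model lines is plain in the text available here, subject to a check of the source PDF, and comparison with the IGA/PGA code makes a slip the likely explanation.

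Under the main assumed split the consequence is a few hundredths of a lesion in one supportive analysis. It could go in either direction, depending on which arm has more early dropout. The size rests on the assumed visit correlation, build-up of effect, timing of dropout and split between arms; none of these is in the documents. No conclusion of the trial would plausibly change. The primary missing-at-random analysis and the IGA/PGA vehicle-based code are unaffected.

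**What to change.** 1. Check the listing in addendum 6.3 against the source PDF.
2. If it reads as here, change one of the two `week_8` vehicle-model lines to `week_4`, leaving the rest of the statement as it is. Each post-baseline visit in the monotone regression step then uses the vehicle model once.
3. Confirm that the production program does the same for facial and truncal counts, and state that the rule in the text governs at every visit.
4. Say in the text that intermittent gaps are filled by the preceding MCMC step from both arms pooled, since the correction leaves that step as it is.

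The cost is one line of code, a sentence or two of text and a program check. The design, sample size and primary analysis do not change.

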#### 6.4. Multiple Imputation – Categorical Sensitivity Analysis

The primary multiple imputation method will treat IGA/PGA as continuous when used as covariates for the logistic regression model. As a sensitivity analysis, the multiple imputation process for IGA/PGA will be repeated treating those predictors as categorical.

First, the pattern of missingness in the data will be evaluated. If the data is not monotone missing, the MCMC method will be used to make it monotone missing. The single chain method will be used, with 200 burn-in iterations and 100 iterations between imputations. Fifty imputations will be created. If all subjects have the same baseline IGA/PGA value, the baseline visit will not be included in the model. The seed number will be 18252. IGA and PGA scores generated as a result of the MCMC method will be rounded prior to the next step; scores will be re-imputed if, after rounding, they are lower than 0 or higher than 4.

Due to the categorical nature of the data, and the rarity of some values of IGA/PGA, there is the potential for convergence issues when using logistic regression with categorical covariates. If this is the case, each week will be imputed sequentially and predictor weeks that cause convergence issues (and thus can't be used as valid predictors) will be dropped.

The model will be chosen by first checking if the inclusion of any covariates causes convergence issues. If so, predictor weeks will be removed from the model and the model rerun until any convergence issues are solved. Earlier weeks will be dropped from the model before later weeks, and combinations of weeks will only be dropped if the removal of only one week does not cause the model to converge. Thus, weeks will be dropped in the following order:

- 1. Week 1
- 2. Week 2
- 3. Week 4
- 4. Week 8
- 5. Weeks 1 and 2
- 6. Weeks 1 and 4
- 7. Weeks 2 and 4
- 8. Weeks 1 and 8
- 9. Weeks 2 and 8
- 10. Weeks 4 and 8

RD.06.SPR.18252 - FINAL October 23, 2017

11. Weeks 1, 2, and 4 12. Weeks 1, 2, and 8 13. Weeks 2, 4, and 8

After each removal, the model will be rerun. The first model that converges will be kept, and the process will restart with the next week until Week 12 is imputed. The final chosen models will be run with seed number 18252. Below is an example of the SAS syntax for the MCMC and logistic MI procedures treating predictor weeks as categorical, with no weeks removed:

```
proc mi data=transI seed=18252 out=mcmcI(rename=_imputation_=imp) nimpute=50 minimum=0 maximum=4 round=1;
mcmc impute=monotone chain=single nbiter=200 niter=100;
var trt01pn baseline week_1 week_2 week_4 week_8 week_12;
run;
```

```
proc mi data=mcmcI seed=18252 out=miI nimpute=1 noprint;
by imp;
class trt01pn baseline week_1 week_2 week_4 week_8 week_12;
var trt01pn baseline week_1 week_2 week_4 week_8 week_12;
monotone logistic(week_1=trt01pn baseline);
monotone logistic(week_2=trt01pn baseline week_1);
monotone logistic(week_4=trt01pn baseline week_1 week_2);
monotone logistic(week_8=trt01pn baseline week_1 week_2 week_4);
monotone logistic(week_12=trt01pn baseline week_1 week_2 week_4 week_8);
run;
```

